2.4 AFA-only Cohort - Participant Inclusion Criteria

178179

182

183

184185

186 187

188

189

190

191

- Individual-level Criteria
- 180 To be eligible, the following inclusion criteria must be met:
- 181 1. Age \geq 18 and < 80 years
 - Individuals <18 years old are not being included because DR is so rare in this age group that the diagnosis of NPDR may be questionable. Individuals ≥ 80 years old are excluded to match the Protocol AF lead study age criterion.
 - 2. Diagnosis of type 2 diabetes mellitus, falling into one of the following categories:
 - For Group 1 participants with DR Severity level 10 to 20 the patient must have been diagnosed ≥15 years ago. If diagnosis of diabetes was <15 years, the participant is not eligible.
 - Any amount of time if DR Severity level ≥ 35 (Groups 2-4)
 - Any one of the following will be considered to be sufficient evidence that diabetes is present:

- 193 Current regular use of oral anti-hyperglycemia agents for the treatment of diabetes.
 - Documented diabetes by American Diabetes Association and/or the World Health Organization criteria.

OR

194 195

196

197

198

199

200

201

204205

210

- Group 5 participants (non-diabetic control group must have generally good health in the opinion of the investigator, no history of documented diabetes or diabetes-related condition, HbA1c levels < 5.7 as confirmed by the central laboratory, must meet none of the exclusion criteria listed below, and must have no evidence of retinal diseases on color fundus photos or OCT.
- 3. Media clarity, pupillary dilation, and study participant cooperation sufficient to obtain adequate fundus photographs, FA, and OCT.
 - Investigator must verify accuracy of OCT scan by ensuring it is centered and of adequate quality (including segmentation line placement)
- 4. Able and willing to provide informed consent and participate (i.e., proficient in written and spoken English, Spanish or other IRB-approved consent language; has the capacity to consent for one's own self).
- 209 5. Able and willing to provide genetics sample.

2.5 Participant Exclusion Criteria

- 1. A condition that, in the opinion of the investigator, would preclude participation in the study such as unable or unwilling to complete all study procedures.
- 2. Participation in an investigational trial that involved treatment within last 30 days, with the exception of the parent Protocol AF.
- 215 3. Known allergy to fluorescein dye.
- 4. Participant has any retinal condition that complicates the diagnosis and grading of DR (e.g., previous therapies (vitreo-retinal surgery, photodynamic therapy)) or participant shows signs of retinal diseases other than DR, such nAMD or MacTel.
- Prior procedures to treat DR (e.g., intraocular anti-VEGF, vitrectomy) are not exclusionary so long as they do not interfere with the evaluation and grading of DR; participants with history of PRP in either eye are excluded since the study does not include DR severity of 60.
- 5. Participant is currently taking or has been taking a PPAR-agonist within the last 90 days.
- 224 6. Participant is currently taking a serine or glycine supplement or has been taking a serine or glycine supplement within the last 60 days.
- 7. Employed in an involved research department or ophthalmologic practice participating in this research.
- 228 8. People who are currently pregnant and/or lactating.

230	2.6 Screening Procedures
231 232 233	After informed consent has been signed, a potential participant will be evaluated for study eligibility through the elicitation of a medical history and performance of an ocular examination by study personnel to screen for exclusionary conditions.
234	2.6.1 Data Collection and Testing
235 236	All testing does not need to be completed on the same day provided it is within the windows specified in the visit procedures. The visit should be scheduled early in the day to accommodate

Chapter 3: Study Visit Procedures 238 239 3.1.1 Visit Procedures 240 The following procedures are needed from participants screened specifically for the AFA cohort 241 to confirm eligibility: 242 If a procedure has been performed using the study technique and by study certified personnel as part of usual care, then it does not need to be repeated specifically for the 243 study if it was performed within the defined time windows specified below. 244 • The testing procedures are detailed in the DRCR Retina Network procedures manuals. 245 246 • Visit procedures will last approximately 4 hours. 247 1. Self-reported demographics (date of birth, sex, race and ethnicity) 248 2. Medical history (pre-existing medical conditions, concomitant medications, as well as ocular 249 diseases, surgeries, and treatment) 250 Medical history will be obtained by medical charts if available at the enrolling site; otherwise, it will be self-reported 251 252 3. Protocol refraction followed by electronic-ETDRS visual acuity testing using the Electronic Visual Acuity Tester or ETDRS charts in both eyes (within prior 8 days of ocular 253 254 examination). 255 Snellen charts are not acceptable for VA testing 256 4. Digital fundus photographs on both eyes using the widest approach available (e.g., Optos ultra-257 widefield imaging device, if available) (within prior 8 days of ocular examination). 258 5. Spectral-domain OCT using Heidelberg Spectralis in both eyes (within prior 8 days of ocular 259 examination). 260 ➤ All OCTs at screening will be sent to a reading center for manual grading 261 Includes additional optic nerve head scan to obtain Retinal Nerve Fiber Layer (RNFL) 262 thickness data. 263 6. Digital FA – only for participants with diabetes 264 > FA will **NOT** be performed on the healthy control group absent a diagnosis of diabetes. 265 FA using the widest approach available (e.g., Optos ultra-widefield imaging device, if available) (within prior 8 days of ocular examination). 266

267 268 269		• The eye with the higher level of DR should always be the transit (rapid series) eye. If both eyes are of equal DR severity, the right eye should be the transit eye.
270 271	7.	Ocular examination on each eye including slit lamp, measurement of intraocular pressure, lens assessment, and dilated ophthalmoscopy (on day of visit).
272	8.	Physical examination to include:
273		Weight and height (within prior 8 days)
274		➤ Blood pressure (within prior 30 days)
275	9.	Fasting blood draw for:
276 277 278		• HbA1c, liver function tests (LFTs), serum creatinine (used for estimated glomerular filtration rate [eGFR]), creatine kinase (CK), complete blood counts (CBC), and lipid panels (within prior 30 days of screening visit, or up to 30 days after screening visit)
279 280 281		➤ The central laboratory must be used — see AFA Coordinator Manual for collection procedure. Includes one sample for HbA1c and CBC tests and one sample for extraction of serum for remaining tests above.
282 283		➤ If HbA1c value is not obtained from central laboratory because sample cannot be analyzed, it does not need to be repeated if available in the prior 3 months.
284		➤ A small snack will be available for the participant after blood draws are performed.
285 286 287		• De-identified serum sample for metabolite measurements (e.g., deoxysphingolipids, serine, other amino acids) using liquid chromatography—mass spectrometry (LC-MS). (within prior 30 days of screening visit, or up to 30 days after screening visit)
288 289 290 291		➤ Includes two 10 mL tubes (or three 7 mL tubes, dependent on the centrifuge) that will be centrifuged for serum extraction and shipped on dry ice. See laboratory procedure manual for details regarding collection, processing, handling, and shipping procedure.
292		Whole blood for genetic testing under this protocol
293 294 295 296 297		Note: this is collection of blood for DNA extraction as part of AFA, the participant can be separately consented to allow this DNA sample to be included in the ongoing repository project (Protocol GEN) but only 1 DNA sample is collected. If the participant does not consent for their sample to be part of the repository (Protocol GEN), then the DNA sample will be destroyed after Protocol AFA analyses end.
298 299	10	. Urine sample (within prior 30 days of screening visit, or up to 30 days after screening visit) for:
300		a. Creatinine and albumin
301 302		b. Pregnancy test for all biological females who are premenopausal and are not surgically sterile

303	11. Additional ancillary testing procedures on each eye (only obtained by a subset of sites) include
304	a. OCT angiography using Heidelberg Spectralis (within prior 8 days of ocular exam)
305 306	b. Contrast sensitivity using the study-provided AST Manifold® (within prior 8 days o ocular exam)
307	3.2 Adverse Event Reporting
308 309 310	Only adverse events related to AFA cohort study participation that required medical intervention will be reported. Bruising or pain at the site of a venipuncture or fingerstick will not be reported as an adverse event unless severe enough that treatment is needed.
311 312	If a participant is enrolled in the parent Protocols AF and GENES, then the AE will be reported under the Protocol AF or Protocol-GENES respectively.
313	3.3 Miscellaneous Considerations
314	3.3.1 Participant Withdrawal
315 316	Participation in the study is voluntary, and a participant may withdraw without completing the study. For participants who withdraw, their data will be used up until the time of withdrawal.
317	3.3.2 Confidentiality
318 319 320 321	For security and confidentiality purposes, participants will be assigned an identifier that will be used instead of their name. Protected health information gathered for this study will be shared with the Coordinating Center, the Jaeb Center for Health Research in Tampa, FL. De-identified participant information may also be provided to research sites involved in the study.
322 323 324 325 326 327 328	The samples to characterize the participants (e.g., HbA1c, LFTs, urine, etc.) will be analyzed at the University of Minnesota, Advanced Research and Diagnostic Laboratory and will not be stored, maintained, and/or used for future research. The samples for metabolomics research will be sent to the central laboratory until a sufficient number has been collected to provide to LMRI in batches. Once provided to LMRI, the de-identified serum samples may be stored, maintained and used for future research. They may also provide de-identified samples to other researchers and industry collaborators.
329 330 331 332 333 334 335 336	The whole blood samples for genetic analyses may be sent to one or more LMRI contracted laboratory (e.g., Biospecimen Processing and Biorepository (BPB) at Fred Hutchinson Cancer Center) facilities within the United States for SNP typing and targeted gene analysis as it pertains to DR. These samples can only be used to perform analyses to meet the research objectives under this protocol. These samples are not permitted to be stored, maintained, and/or used for future research, cannot be used for any other purposes outside of this research protocol, cannot be shared with other researchers or entities outside of LMRI and the laboratories, and may not be used to re-identify participants in accordance with a written agreement with LMRI.
337	3.3.3 Participant Compensation
338	Participant compensation will be specified in the informed consent form.

339	3.3.4 Study Termination
340 341 342	Participant recruitment and enrollment of the AFA-only cohort will end upon enrollment of approximately 200 participants among the planned groups, although enrollment in some cohorts may end sooner depending on feasibility of recruitment and/or the target goal being met
343	3.3.5 Quality Assurance and Monitoring
344 345 346 347 348 349 350 351	Concurrent with the parent Protocol AF and Protocol-GENES, designated personnel from the Coordinating Center (JCHR) will be responsible for maintaining quality assurance (QA) and quality control (QC) systems to ensure that the clinical portion of the trial, and genetic sample processes and procedures, are conducted and data are generated, documented and reported in compliance with the protocol, Good Clinical Practice (GCP) and the applicable regulatory requirements, as well as to ensure that the rights and wellbeing of trial participants are protected and that the reported trial data are accurate, complete, and verifiable. Informed consent processes and adverse events will be prioritized for monitoring.

Chapter 4: Statistical Considerations

The approach to sample size and statistical analyses are summarized below. A detailed statistical analysis plan (SAP) will be written in collaboration with LMRI.

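### The pregnancy test shares the 30-days-before to 30-days-after urine window, so the protocol lets exclusion 8 be tested after study angiography (minor safety and eligibility correction)

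*Protocol*

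**What the plan says.** Section 2.5, exclusion 8, rules out "People who are currently pregnant and/or lactating". Section 3.1.1 opens with "The following procedures are needed from participants screened specifically for the AFA cohort" and gives the purpose as confirming eligibility. Three items in its list matter here.

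- **Item 6:** fluorescein angiography, for participants with diabetes only, within the 8 days before the ocular examination.
- **Item 7:** the ocular examination, on the day of the visit.
- **Item 10:** "Urine sample (within prior 30 days of screening visit, or up to 30 days after screening visit) for" two purposes: (a) creatinine and albumin, and (b) "Pregnancy test for all biological females who are premenopausal and are not surgically sterile". Item 10b carries no further timing.

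Section 2.6.1 adds: "All testing does not need to be completed on the same day provided it is within the windows specified in the visit procedures". Section 2.6 describes the evaluation of "eligibility through the elicitation of a medical history and performance of an ocular examination by study personnel to screen for exclusionary conditions" and does not mention the pregnancy test. Section 3.1.1 also refers to documents outside the protocol: "The testing procedures are detailed in the DRCR Retina Network procedures manuals".

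**The concern.** Item 10b exists to establish whether exclusion 8 applies. Angiography is the procedure in this visit that involves injecting a dye. If the test may be done afterwards, it can come too late to keep a participant who meets exclusion 8 out of that procedure. A test done weeks beforehand does not show status on the day either, and the criterion concerns current pregnancy.

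A wide window suits albumin and creatinine, which describe the participant. It does not suit a test that decides whether someone should be in the study at all. The likeliest explanation is that the two urine tests were placed under one heading for convenience.

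Medical history, taken from charts or self-report, would catch a known pregnancy but not an unrecognised one. What is at stake is participant protection and correct application of an exclusion. No estimate, test or sample size depends on it.

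**Working it through.** No figure in the plan needs reproducing. The check sets the visit windows on one time axis.

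**Inputs**
- Day 0 is the screening visit, taken as the day of the ocular examination (3.1.1, item 7).
- Angiography: day −8 to day 0 (3.1.1, item 6).
- Pregnancy test: day −30 to day +30 (3.1.1, item 10).
- Tests need not share a day (2.6.1).

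**Latest permitted test, counted from angiography** = last test day − angiography day
- Angiography on day 0: 30 − 0 = 30 days afterwards.
- Angiography on day −8: 30 − (−8) = 38 days afterwards.

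**Age of the earliest permitted test at angiography** = angiography day − first test day
- Angiography on day −8: −8 − (−30) = 22 days.
- Angiography on day 0: 0 − (−30) = 30 days.

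These are the outer limits of what the text allows, not typical intervals. Section 3.1.1 puts the visit at about 4 hours, so a single session may be usual.

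**Who is concerned.** By target, the AFA cohort has 160 participants with diabetes in Groups 1 and 4 plus 20 in Group 3: 160 + 20 = 180. This agrees with 200 in total less the 20 in Group 5, who have no angiography. The 180 is only an upper bound, for three reasons:
- Item 10b applies only to those who are premenopausal and not surgically sterile.
- Section 1.4 lets people who failed screening for Protocol AF join without rescreening if samples and tests are complete, so some will have had angiography under that protocol.
- Section 3.1.1 also accepts usual-care procedures: "If a procedure has been performed using the study technique and by study certified personnel as part of usual care, then it does not" have to be repeated when it falls within its window.

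The documents give no age or sex distribution, so the remaining number cannot be calculated.

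**Whether the readable text closes the gap.** Exclusion 8 has no test timing. Section 2.6 names history and ocular examination only. Section 2.6.1 permits separate days. Item 10 expressly allows the period after the visit. None of these puts the test, or its result, before angiography.

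**The case against.** The strongest reply is that the rule may stand elsewhere. Section 1.5.1, on the risks of common procedures, breaks off after its heading in the available text, and the manuals are not shown. Either could require a test before angiography, and sites would then follow that rule within the outer limits of item 10. This stands as a limit on the point: one cannot say that sites are working without a safeguard. It does not rescue item 10, which would still expressly permit what the other text forbids and should be aligned with it.

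A second reply is that nothing readable ties the pregnancy test to angiography. Item 10b has no exception for Group 5, who receive no dye; the exclusion about dye allergy is a separate one; exclusion 8 also covers lactation; and the window matches that of the blood samples, so the test may serve to define the cohort for the metabolite work. This also stands in part. A reader might infer that the protocol exposes pregnant participants to a known harm, but the readable documents state no fluorescein risk in pregnancy and give no reason for exclusion 8. The point is therefore confined to the order of eligibility test and procedure.

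A third reply is that late confirmation is this protocol's habit: HbA1c for Group 5 comes from the central laboratory on blood that may be drawn after the visit, and DR group follows from later Reading Center grading. The parallel is weak, because neither result decides who undergoes an invasive procedure.

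Finally, the study is a non-intervention study rated as minimal risk, and few participants are likely to be concerned. Both are fair, and they keep the point minor.

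**Conclusion.** The point holds as a minor safety and eligibility correction. As written, item 10 permits the test that confirms exclusion 8 to follow study angiography by up to 30 days (angiography on the visit day) or 38 days (angiography on day −8), or to precede it by up to 30 days. This follows from a stated window and not merely from silence.

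The verdict assumes that the screening visit and the ocular examination fall on the same day, and that item 10's window applies to both of its sub-items, as its layout shows. It is subject to section 1.5.1 and the manuals: if they already set the order, what remains is an inconsistency to remove.

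A reader might infer from the width of the window that late testing is common. The documents do not support that, because permitted days say nothing about when sites actually test. Those concerned are premenopausal, non-sterile participants with diabetes whose angiography is performed for the study. Their number is unknown, at most about 180 by target and probably far smaller. The analysis is unaffected.

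**What to change.** Keep the present window for item 10a. Give item 10b its own timing: for premenopausal participants with diabetes who are not surgically sterile, a negative urine pregnancy test, read on site before any angiography performed for the study, for example on the same day. Group 5, the blood draw and angiography already done as usual care within its window can stay as they are. If section 1.5.1 or the manuals already contain such a rule, bring item 10 into line with it.

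The longest permitted delay from study angiography to test would fall from 38 days to 0.

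The cost is one line of protocol text for a test that is already planned. There is one practical burden: section 3.3.2 sends characterisation samples, urine among them, to a central laboratory. If that includes the pregnancy test, sites will need a urine test kit so that the result is known before injection.

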4.1.1 Hypothesis

352

355

358359

360

361

362

363

364

365

366

367

368

Null Hypothesis (H₀): There are no significant genetic or metabolic dysregulations associated with the development and progression of diabetic retinopathy.

Alternative Hypothesis (H_1) : There exist some genetic or metabolic that are associated with the development and progression of diabetic retinopathy.

4.1.2 Sample Size

Table 1. Description of Groups for Analyses from Protocols AF & AFA			
Analysis Group Number	Group Description Participants with Type 2 Diabetes, and worse eye:	Target Number of Participants	
AFA Group 1	Absent of DR, or microaneurysms only (Diabetes ≥15 yrs) (DR severity level 10 to 20)	80	
Protocol AF* Cohort, Group 2	Mild to moderately severe DR (DR severity level 35 to 47)	200	
AFA Group 3	Severe non-proliferative DR (DR severity level 53)	20	
AFA Group 4	Proliferative DR (DR severity level 61 to 81)	80	
AFA Group 5	Absent of any diagnosis of diabetes and absent evidence of retinal disease as determined by color fundus photography and OCT imaging	20	
To	tal Number of Participants in the Analysis Pool (AF & AFA)	400	

*Eligibility is determined by having sufficient serum sample volume and DR Severity Grade, among other criteria (type 2 diabetes, Genetics collection, etc.); the final sample dataset will be adjusted, as needed, for analysis, since some over-enrollment in AFA is possible.

4.1.3 Outcome Measures

The primary outcome measure will be to measure circulating metabolites and quantify genetic markers (see 4.1.3.1) in patients of different DR severity stages (Group 1-4, Table 1) and in healthy control participants.

4.1.3.1 Genetic and Metabolic markers

Genetic markers will be quantified in the form of Single Nucleotide Polymorphisms (SNPs) via
 SNP-Arrays technologies.

371 Metabolic levels will be quantified by mass spectrometry.

372	4.1.3.2 DR severity level
373 374 375	DR severity level will be determined by the Reading Center. Both eyes of a participant will be included in the analysis. The participant's worse eye will be decisive for the final classification of a patient in the above-mentioned categories.
376	4.1.4 Descriptive Statistics
377 378 379 380	Data description will be presented as summarized descriptive statistics (n, mean, standard deviation [SD], median, minimum, maximum and percentages). Variables include demographic data (gender, age, ethnicity), medical history (length of diabetes, medications), HbA1c, BMI, history of neuropathy, DR severity level.
381	4.1.5 Main Statistical Analyses
382 383 384 385 386 387 388	Genetic data will be cleaned by considering call rates, heterozygosity, genetically inferred sex, genotyping batches, missingness, allele frequency, and Hardy-Weinberg disequilibrium. SNP imputation will be performed using the Michigan Imputation Server. Principal component analysis will be used to account for ancestry differences across participants. Genetic relationship between participants will be estimated and accounted for in the analyses. Polygenic risk factors will be constructed by integrating results from external studies performed on T2D, DR, and metabolic levels.
389 390 391 392	Metabolomics data will be cleaned for internal batches used in different mass-spectrometry machines. Outlying samples and metabolites will be discarded as well as metabolites detected in extremely low abundance. Missing metabolic levels will be imputed using multivariate imputation methods. Principal components analysis will be used to visually inspect the data.
393 394 395 396 397 398 399 400	To evaluate the relationships between genetic and metabolic levels with disease severity, different linear regression analyses will be performed. Depending on the data at hand the tools to perform such analyses will vary but in general these will be multivariable linear regression approaches that adjust for potential imbalances of sample covariates as well as genetic ancestry. Intra-sample correlation will be taken into account by using mixed modelling approaches. The results from these associations will be used in several downstream analyses such as enrichment, burden or over-representation analysis. Post-GWAS analyses such as eQTL, TWAS and Mendelian Randomization will also be performed on these data.
401 402 403 404	Significance Level: A significance level, α , of 0.05 will be used for statistical testing of the study endpoints. False discovery rate due to multiple testing will be addressed by correcting the p-values using the Benjamini-Hochberg adaptive false discovery rate procedure. False discovery rate threshold will be set to 5% to claim significance.
405 406 407 408 409 410 411 412	Multi-omics analysis will be performed by integrating all significant markers found across the genetic and metabolic landscapes. Multivariate co-regulation networks will be constructed to understand potential biological mechanisms underpinning DR. Multivariate clustering techniques will be used to investigate whether combinations of multi-omics factors are able to better stratify across DR severity groups. Prediction models will be built to understand potential diagnostic and prognostic tools. Linear modelling techniques will be implemented to understand potential causative networks across the different 'Omics markers as well as to assess potential interactions across different markers.

- 413 Finally, external data (such as data from UK Biobank or the MacTel consortium studies) will be
- 414 integrated into our study to further expand the discovery potential for this study.

416 Chapter 5: REFERENCES

427

428

429

430

434

435

436

437

438

439

440

441

442

443

444

 [published Online First: 1994/09/01]

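### Section 4.1.5 chooses markers by their association with DR severity, then uses them to stratify and predict DR severity, with no stated separation of selection from evaluation

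*Protocol*

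**What the plan says.** Section 4.1.5 of the protocol sets out a sequence.

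1. Genetic and metabolic markers are related to disease severity by regression: "in general these will be multivariable linear regression approaches that adjust for potential imbalances of sample covariates as well as genetic ancestry".
2. The threshold is fixed: "A significance level, α , of 0.05 will be used for statistical testing of the study endpoints", with Benjamini-Hochberg correction, and "False discovery rate threshold will be set to 5% to claim significance".
3. The markers that pass go forward: "Multi-omics analysis will be performed by integrating all significant markers found across the genetic and metabolic landscapes".
4. The same paragraph gives two later uses: "Multivariate clustering techniques will be used to investigate whether combinations of multi-omics factors are able to better stratify across DR severity groups" and "Prediction models will be built to understand potential diagnostic and prognostic tools".
5. Data from outside sources such as UK Biobank or the MacTel studies are to be "integrated into our study to further expand the discovery potential for this study".

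One set of predictors comes from elsewhere: "Polygenic risk factors will be constructed by integrating results from external studies performed on T2D, DR, and metabolic levels". Chapter 4 describes itself as a summary and leaves detail to a SAP that is still to be written.

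**The concern.** The multi-omics stage receives markers because they varied with severity in this study, and it is then judged on whether it separates severity. If the same participants serve both purposes, part of the separation is there by construction. A marker that passes a strict threshold tends to have an observed association larger than its true one, and a few pass by chance.

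The FDR rule limits the share of false markers among those selected. It does not correct the exaggerated effects of the true ones. Cross-validating only the final model does not solve this either, because the held-out participants have already helped to choose the markers.

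At stake is how far any claim of a diagnostic or prognostic tool can be believed. The only independent data that the protocol names are given to discovery, so nothing in the text as it stands would reveal the optimism.

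**Working it through.** **The plan's own figure.** The protocol gives no power, effect size or discrimination target. The one figure that can be checked is the pool in Table 1: 80 + 200 + 20 + 80 + 20 = 400, which reproduces. The four diabetic groups total 80 + 200 + 20 + 80 = 380.

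**Inputs from the protocol.** Group sizes of 80/200/20/80 (Table 1 and section 2.3); selection by linear regression on severity; 5% FDR (section 4.1.5).

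**Assumptions not in the documents.** 500 or 5,000 independent markers; 0 to 30 of them truly related to severity, with correlation r of 0.15 to 0.30; groups scored 1 to 4; no covariates; standard rather than adaptive Benjamini-Hochberg; AUC for Group 4 against Group 1 as the measure. Group 5 is left out.

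**Formulas.**
- True marker: x = r·z + √(1 − r²)·e, where z is standardised severity and e is standard normal.
- Test: t = R·√((n − 2)/(1 − R²)), where R is the sample correlation and n = 380.
- Selection: the largest k for which the k-th smallest p-value is at most 0.05·k/m, where m is the number of markers.
- Model: least squares of severity on the selected markers.
- AUC = (rank sum of Group 4 − 80·81/2)/(80·80).

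**Why weak markers suffer most.** With m = 500, the first Benjamini-Hochberg step is 0.05/500 = 0.0001. At 378 degrees of freedom this needs |t| = 3.93, so |R| = 3.93/√(378 + 3.93²) = 0.198. When few markers pass, one with true r = 0.15 is selected mainly in samples where its correlation happens to reach about 0.20.

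**Results.** Mean AUC over the datasets in which at least one marker was selected:

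| Setting | Any marker selected | Apparent | CV after selection | Selection inside folds | New participants |
|---|---|---|---|---|---|
| 500 markers, 5 true, r = 0.15 | 69% | 0.731 | 0.722 | 0.628 | 0.645 |
| 500 markers, 30 true, r = 0.15 | 100% | 0.929 | 0.909 | 0.812 | 0.843 |
| 500 markers, 10 true, r = 0.20 | 100% | 0.905 | 0.888 | 0.845 | 0.862 |
| 5,000 markers, 20 true, r = 0.20 | 100% | 0.958 | 0.946 | 0.884 | 0.909 |
| 500 markers, 10 true, r = 0.30 | 100% | 0.984 | 0.979 | 0.976 | 0.977 |
| 500 markers, none true | 4.8% | 0.682 | 0.676 | 0.562 | 0.503 |
| 5,000 markers, none true | 4.0% | 0.689 | 0.685 | 0.556 | 0.499 |

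Each setting used 30 to 1,000 datasets (30 for 5,000 markers with 20 true), so the third decimal is not firm.

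**Apparent minus new participants.**
- Weak: 0.731 − 0.645 = 0.086 and 0.929 − 0.843 = 0.086.
- Moderate: 0.905 − 0.862 = 0.043 and 0.958 − 0.909 = 0.049.
- Strong: 0.984 − 0.977 = 0.007.

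**Cross-validation begun after selection.** Wherever there was true signal, it lowered the apparent AUC by 0.005 to 0.020. The excess that remained was 0.077 and 0.066 (weak), 0.026 and 0.037 (moderate) and 0.002 (strong).

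**Selection inside folds.** Wherever there was true signal, the estimate was 0.001 to 0.031 below the value in new participants, so it errs slightly on the cautious side. In the rare no-signal datasets that selected something, it still read about 0.56 against 0.50.

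**The case against.** The strongest reply is that internal validation belongs in the SAP. Chapter 4 says that a detailed plan will follow, and fold structure, held-out reporting and performance measures are ordinary SAP content. Their absence from the protocol is not an error, and that part of the reply stands. What remains is the order of operations, which the protocol does state: the multi-omics stage starts from markers already declared significant. A SAP that followed this literally and cross-validated only the final model would look careful and still be biased.

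A reader might also infer more than the text says.

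- *Selection uses every participant, and the prediction models use only the selected markers.* Both are natural readings of a single pool with no split, but neither is stated. The prediction sentence names no predictor set.
- *Reported discrimination will be inflated.* The protocol names no discrimination measure and does not say that same-data performance will be reported. The bias is conditional on how the plan is carried out.
- *Pure noise could readily pass for a strong diagnostic tool.* That could follow from selecting at an uncorrected p below 0.05, which is not the protocol's rule. Under 5% FDR with no signal, nothing is selected in about 95% of datasets.
- *All predictors are exposed.* Polygenic scores weighted from external studies are not chosen in this dataset and escape this bias.

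Finally, prediction is a downstream, exploratory use. The primary outcome measure in section 4.1.3 and the association objectives in section 1.3 do not depend on it.

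**Conclusion.** The point holds conditionally. As written, section 4.1.5 uses association with severity to choose markers and separation of severity to judge them, with no stated boundary between the two and with external data assigned to discovery. Carried out literally in one pool, discrimination would be biased upward, and cross-validation begun after selection would leave much of the bias in place when markers are weak or moderate.

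The documents do not fix the size. Under the stated assumptions it runs from about 0.09 AUC for weak markers, through 0.04 to 0.05 for moderate ones, to under 0.01 for strong ones. Section 1.1 says that the link between sphingolipid metabolism and DR has not yet been examined, so strong effects cannot be taken for granted. The association results are not in question. This is worth correcting before analysis, but it concerns a secondary, exploratory stage.

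**What to change.** Add to section 4.1.5, and carry into the SAP, wording to this effect: for clustering and prediction, the FDR marker selection and any other step that uses DR severity is repeated inside each training fold, with folds stratified by severity group; or performance is assessed in held-out or external participants not used for selection. Held-out performance is reported as the result, and any same-data performance is labelled apparent. If an external source carries the same markers, it could be reserved for this purpose.

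Steps that do not use severity, such as batch correction, need not be refitted in each fold on this account. The fix also needs no clinical comparator model. One that included diabetes duration would raise its own difficulty, because Group 1 must have at least 15 years of diabetes and Groups 2 to 4 need no minimum, so duration partly encodes group membership.

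No new participants or samples are needed if folds are used. The costs are computing time, AUCs that are lower and slightly conservative, and imprecise estimates for Group 3, where 20 participants give about 2 per fold in ten-fold cross-validation (20/10).
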